2.3.3 ADA population

ADA population is defined as:

- All participants from the safety population with at least 1 post-Baseline valid ADA sample after drug administration.

2.3.4 PK population

PK population is defined as:

- All participants from the safety population with at least 1 measurable serum efpeglenatide concentration available for PK analysis.

2.4 STATISTICAL METHODS

In general, descriptive statistics of quantitative efficacy and safety endpoints (result and change from baseline) by scheduled visit will be provided on observed cases (OC), ie, only including participants having a non-missing assessment at a specific visit.

2.4.1 Demographics and baseline characteristics

Parameters described in [Section 2.1.1](#) will be summarized on the ITT population by randomized treatment group and overall using descriptive statistics.

Continuous data will be summarized using the number of available data, mean, standard deviation (SD), median, minimum, and maximum for each treatment group. Categorical and ordinal data will be summarized using the number and percentage of participants in each treatment group. Missing data will not be categorized in the summaries.

Medical history will be summarized on the ITT population by treatment group (and overall), primary SOC, and HLT, with events sorted by primary SOC in internationally agreed order and decreasing frequency of HLT in the overall group.

Technical formulas are described in [Section 2.5.1](#).

P-values on demographic and Baseline characteristic data will not be calculated.

2.4.2 Prior or concomitant medications

The prior, concomitant, and post-treatment medications will be presented for the ITT population and the following two summaries will be produced for each:

- All medications (excluding anti-diabetic), and
- Anti-diabetic medications.

Medications will be summarized by treatment group (and overall) according to the WHO-DD, considering the first digit of the ATC class (anatomic category) and the first 3 digits of the ATC class (therapeutic category). Anti-diabetic medications will be summarized by the ATC categories, pharmacological class and chemical class. Prohibited medications will be summarized by category of prohibited medication and chemical class.

All ATC codes corresponding to a medication will be summarized, and participants will be counted once in each ATC category (anatomic or therapeutic) linked to the medication. Therefore, participants may be counted several times for the same medication. The table for prior medications will be sorted by decreasing frequency of ATC followed by all other therapeutic classes based on the overall incidence across treatment group. In case of equal frequency regarding ATCs (anatomic or therapeutic categories), alphabetical order will be used.

The tables for concomitant and posttreatment medications will be sorted by decreasing frequency of ATC followed by all other therapeutic classes based on the incidence in the Efpeglenatide 6 mg treatment group. In case of equal frequency regarding ATCs (anatomic or therapeutic categories), alphabetical order will be used.

Similar to concomitant medications, prohibited medications will be sorted by decreasing frequency of ATC followed by all other therapeutic classes based on the incidence in the Efpeglenatide 6 mg treatment group.

2.4.3 Extent of investigational medicinal product exposure and compliance

The extent of IMP exposure and compliance will be assessed and summarized by actual treatment within the safety population ([Section 2.3.2](#)).

2.4.3.1 *Extent of investigational medicinal product exposure*

The extent of IMP exposure will be assessed by cumulative exposure (patient years), duration (days), and category (weeks).

Duration of IMP exposure is defined as last dose date – first dose date + 7, regardless of unplanned intermittent discontinuations (see [Section 2.5.3](#) for calculation in case of missing or incomplete data).

Duration of IMP exposure will be summarized descriptively as a quantitative variable (number, mean, SD, median, minimum, and maximum). In addition, duration of treatment exposure will also be summarized categorically by numbers and percentages for each of the following

categories and cumulatively according to these categories: 1 to 2 weeks, 3 to 4 weeks, 5 to 8 weeks, 9 to 12 weeks, 13 to 18 weeks, 19 to 24 weeks, 25 to 30 weeks, 31 to 43 weeks, 44 to 56 weeks, and >56 weeks. The duration of treatment exposure in weeks will be the duration (in days)/7, rounded to the nearest integer.

Duration of study will be summarized separately and analyzed descriptively as a quantitative variable (number, mean, SD, median, minimum, and maximum). The duration of study is defined as date of completion or discontinuation – date of first dose of IP + 1. In the case of not treated participants, the randomization date will be used for calculation purposes.

2.4.3.2 *Compliance*

A given administration will be considered noncompliant if the participant did not take the planned dose of treatment as required by the protocol. No imputation will be made for participants with missing or incomplete data.

Percentage of compliance for a participant will be defined as the number of injections (partial injection will be counted as 1 injection) that the participant was compliant divided by the total number of injections that the participant was planned to take during the treatment period defined from the first to the last dose injection. Number of planned injections is calculated as following:

$$1 + (\text{last dose date} - \text{first dose date} + 1) / 7, \text{ rounded to the nearest integer.}$$

Treatment compliance will be summarized descriptively as quantitative variables (number, mean, SD, median, minimum, and maximum). The percentage of participants whose compliance is <60, ≥60 and <80, ≥80% and ≤100%, or >100% will be summarized.

Cases of overdose will constitute AESIs and will be listed as such.

2.4.3.3 *Frequency of injections*

The frequency of injections during the whole on-treatment period will be summarized separately by time of day (morning, afternoon, evening, night) and location of injection (Abdomen, Other, Missing). For analysis purposes, morning is defined as the time between 06:00-11:59, afternoon as between 12:00-17:59, evening as between 18:00-23:59, and night as between 00:00-05:59.

2.4.4 *Analyses of efficacy endpoints*

Efficacy analyses will be performed on the ITT population using efficacy assessment collected during the study, including those obtained after IMP discontinuation and/or introduction of rescue therapy, unless otherwise specified (see [Section 2.5.4](#)).

Due to COVID-19 pandemic, participants may not be able to maintain their regular clinical visits according to the study protocol, with the closure of facilities, safety concern for the participants to go to the sites, unavailability of the investigators for treating participants, interruption of transportation or other COVID-19 related reasons. Data missingness due to these reasons is likely to be missing at random. For a continuous endpoint, all observed data of participants within the

same treatment group can be used for imputation in an MAR approach. Sensitivity analyses will be performed to take into consideration of the impact of COVID-19 if the number of participants with missing endpoint data due to COVID-19 is above the threshold as specified in the following sections.

Of note, it is unlikely that the efficacy analyses at Week 30 in EFC14822 would be impacted by COVID-19 as the last Week 30 visit was performed on 29Jan2020. However, the efficacy analyses at Week 56 is likely to be impacted.

2.4.4.1 Analysis of primary efficacy endpoint

The statistical test will be 2-sided tests at a nominal 5% significance level.

Hypothesis Testing of the Primary Endpoint

For the primary efficacy variable of change from Baseline to Week 30 in HbA1c (%), the following statistical null hypothesis and alternative will be tested for each efpeglenatide dose:

- H0: No population LS mean treatment difference in reduction in HbA1c from Baseline;
- H1: Efpeglenatide has a higher population LS mean reduction in HbA1c from Baseline than placebo.

Primary Analysis

The statistical analysis for the primary endpoint is described below.

The Baseline value is defined in [Section 2.1.1](#).

The primary analysis will be an analysis of covariance (ANCOVA) modeling with missing values imputed based upon retrieved dropouts in 2 separates parts as follows:

1. Missing endpoint data in participants who prematurely discontinue the study treatment before the Week-30 visit will be imputed using a model built separately in each arm and estimated from participants in the same treatment arm who prematurely discontinue the study treatment before the Week-30 visit but have the measurement for the endpoint (retrieved dropouts). Considering that the number of participants in each treatment arm who discontinue the study treatment but have the measurement for the endpoint is expected to be small, a simple imputation model will be used, where only the Hb1Ac baseline measurements are included as the predictor. Each treatment group will have their own imputation model. Missing data will be imputed using the regression method.
2. Missing endpoint data in all participants, including those in the efpeglenatide arms, who stay on the study treatment until the Week-30 visit will be imputed separately. The washout-imputation method will be used, where missing endpoint data in the efpeglenatide arms, as well as the missing data in the placebo arm, are imputed from a model estimated from participants in the placebo group with endpoint data without including any intermediate values. The imputation model will include the randomization strata and corresponding Hb1Ac baseline values. Missing data will be imputed using the regression method.

In this analysis, missing endpoint values will be imputed 10 000 times to generate 10 000 data sets with complete data. The completed data sets will be analyzed using an ANCOVA model with the treatment group (efpeglenatide 2, 4, or 6 mg, or placebo), randomization stratum of Screening HbA1c ($<8.0, \geq 8.0\%$), BMI at Visit 3 ($<30, \geq 30 \text{ kg/m}^2$), and geographical region as fixed classification effects, and Baseline HbA1c value as a continuous covariate.

For subjects with missing efficacy endpoint data at Baseline, values will be imputed using the population mean at Baseline.

SAS pseudo-codes are provided in [Appendix A](#).

The results from the 10 000 analyses will be combined using Rubin's formula, to provide the adjusted mean change in HbA1c from Baseline to Week 30 (regardless of treatment discontinuation or initiation of rescue therapy) for each treatment group, as well as the difference between each efpeglenatide dose and placebo and the 95% confidence interval (CI) for the difference. This will be implemented using MIANALYZE procedure in SAS.

A hierarchical procedure will be applied to adjust for the multiplicity of comparison on the primary endpoint:

- First, the highest dose of efpeglenatide (6 mg) will be compared to placebo to demonstrate superiority of this dose to placebo
- If superiority is demonstrated for efpeglenatide 6 mg, the superiority of 4 mg dose of efpeglenatide to placebo will be tested
- If superiority is also demonstrated for 4 mg dose, the lowest dose (2 mg) will be tested for superiority to placebo

When the superiority is not obtained in a step, the sequential testing procedure will be stopped.

As noted, the number of retrieved dropouts is expected to be small, and there may not have sufficient data to support the imputation approach in item 1 described above. If there are less than 5 participants in any arms who prematurely discontinue the study treatment before the endpoint visit but have the measurement for the endpoint, a back-up imputation method for the primary efficacy analysis will be used. In particular, missing endpoint data in all participants in both efpeglenatide and placebo groups, regardless of staying on the study treatment or not, will be imputed using a model estimated from participants in the placebo group with endpoint data without including any intermediate values, where randomization strata and corresponding baseline values are included as the predictors. Missing data will be imputed using the regression method.

Sensitivity Analysis

Tipping point analysis

Tipping point analysis based on the same multiple imputation (MI) method as applied above will be performed to examine the robustness of the results from the primary analysis. A penalty δ will be applied to participants in the efpeglenatide group who have no HbA1C data at Week 30. The penalty will be gradually increased to determine at which level (if any) the conclusion of the

analyses in terms of statistical significance is changed for each efpeglenatide dose group. The tipping point is the penalty level at which the magnitude of efficacy reduction in participants without HbA1c data at Week 30 creates a shift in the treatment effect of efpeglenatide from being statistically significantly better than placebo to a non-statistically significant effect. The penalty δ will start at 0 and increase by 0.1 (unit: %) until non-statistical significance is found. Least square mean difference between each efpeglenatide dose and placebo and its associated p-value will be provided for each penalty level.

Analysis on completers

For participants in ITT population who completed the 30-week core treatment period and did not start any rescue therapy before the end of the period, the primary endpoint will be assessed too by the same ANCOVA model as used for the primary analysis using the observed values.

Assessment of missing data

The availability of primary and secondary efficacy data (yes, no) at the endpoint visit (Week 30 or Week 56) will be summarized by treatment status (discontinued, completed) and by treatment group.

Assessment of treatment effect by subgroup

Primary efficacy endpoint will be further analyzed to examine the consistency of the treatment effect across the subgroups defined by the following Screening or Baseline covariates:

- Race (White, Black or African American, Asian, Other) (any race groups with fewer than 5 participants may be combined with “Other” category as appropriate)

Note: For all efficacy and safety subgroup analyses, race groups “Not reported”, “Unknown”, and participants who report more than one race will be considered “Other”.

- Ethnicity (Hispanic or Latino, Not Hispanic or Latino)
- Age group (<50, \geq 50 to <65, \geq 65)
- Gender (Male, Female)
- Duration of diabetes (<10, \geq 10 years)
- Baseline HbA1c (<8.0, \geq 8.0%)
- Baseline BMI (<30, \geq 30 to <40, \geq 40 kg/m²)
- Region (North America, Western Europe, Eastern Europe)
- Baseline estimated GFR categories (mL/min/1.73m²): (<60; \geq 60 to <90; \geq 90)

The treatment effects (efpeglenatide 2, 4, or 6 mg, versus placebo) across the subgroups defined for each of these factors will be estimated for the change from Baseline to Week 30 in HbA1c in the ITT population, and using the same imputation approach (retrieve dropout) as applied to the primary analysis of the primary efficacy endpoint. The ANCOVA model will include treatment groups (efpeglenatide 2, 4, or 6 mg, placebo) and randomization stratum of Screening HbA1c

($<8.0, \geq 8.0\%$), randomization stratum of Visit 3 (Baseline, Day 1) BMI ($<30, \geq 30 \text{ kg/m}^2$), subgroup factor, treatment-by-subgroup factor, and region as fixed factors and using Baseline HbA1c value as a covariate. The adjusted estimates of treatment mean differences (each efpeglenatide dose versus placebo) with SE and 95% CIs will be provided as appropriate across the subgroups. A graphical presentation of the results (ie, forest plot) will also be provided.

In the case that the subgroup factor (eg, Baseline HbA1c, Baseline BMI) is identical or similar to a randomization strata factor, only the subgroup factor (as a single factor or an interaction term) will be included in the model in order to avoid the issue of collinearity in the analysis. The corresponding strata factor will not be included in the model.

Descriptive statistics for change from baseline in HbA1c to Week 30 will be presented by ADA status for the 3 efpeglenatide groups:

- ADA status (positive, negative) at Baseline, if $\geq 5\%$ of participants are ADA positive;
- Treatment-emergent ADA status (positive, negative).

Summary statistics at scheduled visits

Summary statistics (for Screening value, Baseline value, observed values, and observed changes from Baseline) at scheduled visits will be provided by treatment group for HbA1c value over the treatment period. The last on-treatment value will be presented in a separate row. The summary will include the number of observations, mean, SD, SE, minimum, median, and maximum. Graphical presentations will also be used to examine trends over time using mean values ($\pm \text{SE}$) and mean changes from Baseline ($\pm \text{SE}$) at each of the scheduled visits (using OC).

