1.3 DETERMINATION OF SAMPLE SIZE

The sample size calculations are performed based on the primary endpoint, change in HbA1c (%) from Baseline to Week 30.

A sample size of approximately 100 participants per arm (ie, 100 participants for each of the efpeglenatide doses and 100 for the placebo group) has 89% (96%) power to detect a treatment difference of -0.5% (-0.6%) between each dose of efpeglenatide and placebo in HbA1c change from Baseline to Week 30, assuming a common standard deviation of 1.1% (2-sided, alpha=0.05) for each comparison.

Hence, there are 4 parallel dosing arms:

- Efpeglenatide 2 mg, N=100;
- Efpeglenatide 4 mg, N=100;
- Efpeglenatide 6 mg, N=100;
- Efpeglenatide placebo, N=100.

Hierarchical procedure will be done to adjust the multiplicity of comparison.

[figure not shown]

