 - Step 2: Based on the MONOTONE data sets obtained from Step 1, build the imputation model using the regression method sequentially for each scheduled visit. The imputation model will include the randomization stratum of Hba1c value at Screening ($<8.0, \geq 8.0\%$), the randomization stratum of Visit 3 (Baseline, Day 1) BMI ($<30, \geq 30 \text{ kg/m}^2$), corresponding baseline values and preceding scheduled postbaseline values.

Similar to what is specified in [Section 2.4.4.1](#), only Step 2 a) and b) will be applied if there are insufficient data to support the imputation approach in Step 1 above (ie, fewer than 5 participants in any arms who prematurely discontinue the study treatment before the endpoint visit but have the measurement for the endpoint).

Participants without data at the endpoint visit will be summarized by treatment status (discontinued, completed) and by impact of COVID-19 on participant (yes, no) for each treatment group.

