2.4.4.3 Multiplicity issues

To protect the family-wise error rate for the secondary endpoint, the adjustment for multiplicity of comparison will be applied.

For secondary endpoints, a step-down testing procedure will be applied. For the primary efficacy endpoint (change from Baseline to Week 30 in HbA1c), the 3 efpeglenatide doses will be tested in the order of 6 mg, 4 mg, and 2 mg. Once the primary endpoint is statistically significant at $\alpha=0.05$ (2-sided) for all 3 efpeglenatide doses, a hierarchical testing procedure will be performed to test the following study secondary efficacy endpoints by the following prioritized order:

1. HbA1c $<7\%$ at Week 30 for efpeglenatide 6 mg versus placebo (yes/no)
2. HbA1c $<7\%$ at Week 30 for efpeglenatide 4 mg versus placebo (yes/no)
3. Change from Baseline to Week 30 in body weight (kg) for efpeglenatide 6 mg versus placebo

4. Change from Baseline to Week 30 in body weight (kg) for efpeglenatide 4 mg versus placebo
5. HbA1c <7% at Week 30 for efpeglenatide 2 mg versus placebo (yes/no)
6. Change from Baseline to Week 30 in FPG (mmol/L, mg/dL) for efpeglenatide 6 mg versus placebo
7. Change from Baseline to Week 30 in FPG (mmol/L, mg/dL) for efpeglenatide 4 mg versus placebo
8. Change from Baseline to Week 56 in body weight (kg) for efpeglenatide 6 mg versus placebo
9. Change from Baseline to Week 56 in HbA1c (%) for efpeglenatide 6 mg versus placebo
10. Change from Baseline to Week 56 in body weight (kg) for efpeglenatide 4 mg versus placebo
11. Change from Baseline to Week 56 in HbA1c (%) for efpeglenatide 4 mg versus placebo
12. Change from Baseline to Week 56 in HbA1c (%) for efpeglenatide 2 mg versus placebo
13. Change from Baseline to Week 56 in body weight (kg) for efpeglenatide 2 mg versus placebo

Based on the hierarchical testing above, the testing will stop as soon as an endpoint for an efpeglenatide dose is found to be not statistically significant at $\alpha=0.05$ (2-sided). No multiplicity adjustment will be made on other secondary efficacy variables or the comparison of other efpeglenatide dose versus placebo than mentioned above.

2.4.4.4 *Exploratory efficacy analysis*

2.4.4.4.1 *HbA1c <7.0 % at Week 56 (yes/no)*

Proportions of participants achieving HbA1c target values of <7.0% at Week 56 will be analyzed by same approach described in secondary endpoint: HbA1c < 7% at Week 30.

2.4.4.4.2 *Change in FPG from baseline to Week 56*

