Appendix A Efficacy analysis SAS pseudo code

Primary Analysis missing data imputation:

1. Multiple imputations in participants who prematurely discontinued the study treatment before the Week-30 visit:

```
proc mi data= data_IN out= data_OUT_DISC n impute=10000 seed=14822;  
    where PEOTF30L = "Y";  
    by ARM;  
    var BASE AVAL_W30;  
    monotone regression (AVAL_W30= BASE );  
run;
```

2. Multiple imputations in participants who stay on the study treatment until the Week-30 visit

```
proc mi data= data_IN out= data_OUT_COMPL_MI n impute=10000 seed=14822;  
    where PEOT30FL='N' and (ARM='Placebo' or (ARM ne 'Placebo' and AVAL_W30 =. ));  
    class HbA1c strata BMI strata;  
    var HbA1c strata BMI strata base AVAL_W30;  
    monotone regression (AVAL_W30 = HbA1c strata BMI strata BASE );  
run;
```

3. Transform dataset of EFPEG participants who are under treatment at Week 30 visit with a collected endpoint to have 10 000 replications.

```
Data data_OUT_COMPL_EFPEG;  
Set data_IN (where=( PEOT30FL='N' and ARM ne 'Placebo' and AVAL_W30 ne .));  
n_imput=1;  
%do i = 1 %to 10 000;  
n_imput=n_imput+1;  
%end;  
run;
```

4. Combine multiple imputations from the three subsets of participants

```
Data  dataMI;  
set   data_OUT_DISC  
      data_OUT_COMPL_MI  
      data_OUT_COMPL_EFPEG;  
run;
```

Back-up plan:

```
Data  data_OUT_COMPL_EFPEG;  
Set   data_IN (where=( ARM ne 'Placebo' and AVAL_W30 ne .);  
n_imput=1;  
%do i = 1 %to 10 000;  
n_imput=n_imput+1;  
%end;  
run;  
  
proc mi data =data_IN out=data_OUT_MI nimpute=10000 seed=14822;  
  where ARM='Placebo' or (ARM ne 'Placebo' and AVAL_W30 =.);  
  class HbA1c_strata BMI_strata;  
  var HbA1c_strata BMI_strata base AVAL_W30;  
  monotone regression (AVAL_W30 = HbA1c_strata BMI_strata BASE );  
run;  
data  dataMI;  
set   data_OUT_MI  
      data_OUT_COMPL_EFPEG;  
run;
```

Sensitivity analysis (*If more than 10 missing endpoint data impacted by COVID-19*):

```
#3 DATA data_OUT_COMPL;  
      Set data_IN (where = (PEOTF56L='N' and W56_missing = "N"));  
      _imputation_=0;  
      do i = 1 to 10 000;  
      _imputation_=imputation_+1;  
      output;  
      end;  
run;
```

#1 Multiple imputations in participants who prematurely discontinued the study treatment before the Week 56 visit:

```
proc mi data= data_IN out=data_OUT_DISC nimpute=10000 seed=14822;  
      where PEOTF56L = "Y";  
      by ARM;  
      var BASE AVAL_W56;  

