      monotone regression (AVAL_W56= BASE );  
run;
```

```
#2a proc mi data      =data_IN out=data_OUT_MI nimpute=10000 seed=14822;  
      where PEOT56FL='N' and ((ARM='Placebo' and W56_missing = "N") or (ARM = 'Placebo' and W56_missing = "Y" and  
COVID = "N") or (ARM ne 'Placebo' and W56_missing = "Y" and COVID = "N"));  
      class HbA1c_strata BMI_strata;  
      var HbA1c_strata BMI_strata base AVAL_W56;  
      monotone regression (AVAL_W56 = HbA1c_strata BMI_strata BASE);  
run;
```

```
data data_OUT_MI_MISSING;
  set data_OUT_MI;
  if W56_missing = "Y";
run;

proc sort data= data_IN out=data_IN_COVID;
  by ARM;
run;

#2b step 1
proc mi data  =data_IN_COVID out= monotone nimpute=10000 seed=14822;
  by ARM;
  where PEOT56FL='N' and (W56_missing ne "Y" or (W56_missing = "Y" and COVID="Y"));
  mcmc chain=multiple impute=monotone
  var BASE AVAL_W12 AVAL_W30 AVAL_W43 AVAL_W56;
  /* For body weight, include Weeks 4, 8, 12, 24, 30, 43, and 56 */
run;

#2b step2
proc mi data= monotone out= OUT_MI_MISSING_COVID nimpute=1 seed=14822;
  by ARM _imputation_;
  class HbA1c_strata BMI_strata;
  monotone reg ( / details);
  var HbA1c_strata BMI_strata BASE AVAL_W12 AVAL_W30 AVAL_W43 AVAL_W56;
  /* For body weight, include Weeks 4, 8, 12, 24, 30, 43, and 56 */
run;
```

```
data data_OUT_MI_MISSING_COVID;  
  set OUT_MI_MISSING_COVID;  
  if W56_missing = "Y";  
run;
```

```
data  dataMI;  
set   data_OUT_DISC  
      data_OUT_MI_MISSING  
      data_OUT_MI_MISSING_COVID  
      data_OUT_COMPL;  
run;
```

In this sample SAS® (version 9.4) code:

- DATA_IN is the input dataset including one observation per participant in the ITT population with Baseline HbA1c value and change from baseline at Week 30.
- data_OUT_DISC is the output dataset including observed and imputed data for participants who have prematurely discontinued the treatment.
- data_OUT_COMPL_MI is the output dataset including observed and imputed data for all Placebo participants who have completed the 30-week study treatment period and all Efpeg participants who have completed the 30-week study treatment period without Week 30 endpoint.
- Data_OUT_COMPL_EFPEG is the output dataset included observed data for Efpeg participants who have completed the 30-week study treatment period and have Week 30 endpoint.
- DataMI is the final output containing 10,000 lines by participant with all observed and imputed data used for the ANCOVA.

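### Should the retrieved-dropout imputation pool the arms, given that a separate model in each arm may rest on only 5 people?

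*SAP*

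**What the plan says.** SAP 2.4.4.1 (Primary Analysis, item 1) handles participants who stop treatment before Week 30 and have no Week 30 HbA1c. Their values come from a regression on retrieved dropouts, with baseline HbA1c as the only predictor: "Each treatment group will have their own imputation model". Protocol Table 5 and the protocol synopsis say the same. In SAP Appendix A, step 1 runs `by ARM` with "monotone regression (AVAL_W30= BASE" as the model.

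The rule has a floor: "If there are less than 5 participants in any arms who prematurely discontinue the study treatment before the endpoint visit" but do have the endpoint, a placebo-based back-up replaces it. Results from 10 000 imputations are combined with Rubin's formula.

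The Week 56 COVID-19 sensitivity analysis (SAP 2.4.4.2.2) repeats the method. Its code is headed "1 Multiple imputations in participants who prematurely discontinued the study treatment before the Week 56 visit" and uses "monotone regression (AVAL_W56= BASE", with the same floor: "fewer than 5 participants in any arms who prematurely discontinue the study treatment before the endpoint visit".

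Both documents say that few retrieved dropouts are expected. Neither gives a discontinuation or retrieval rate.

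**The concern.** The floor admits very thin models. With 5 retrieved dropouts and two regression parameters, 3 residual degrees of freedom remain. Proper regression imputation then draws the residual variance from a heavy-tailed distribution whose mean is well above the estimate. Rubin's standard error inherits the excess, and 10 000 imputations do not remove it.

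The loss would fall on the primary test. Secondary testing opens only when the primary endpoint is significant "for all 3 efpeglenatide doses, a hierarchical testing procedure will be performed" (SAP 2.4.4.3). Placebo is common to all three comparisons, so one thin placebo regression weakens each of them. The continuous secondary endpoints reuse the method. SAP 1.3 makes no stated allowance for missing data.

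One regression over all retrieved dropouts, with arm as a factor, looks like an easy remedy: imputed means stay arm-specific and the variance is estimated on many more degrees of freedom.

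**Working it through.** **Planned power.** SAP 1.3 states that 100 per arm "has 89% (96%) power to detect a treatment difference of -0.5% (-0.6%) between each dose of efpeglenatide and placebo", with SD 1.1 and two-sided alpha 0.05. SE = 1.1 x sqrt(2/100) = 0.1556. At -0.5: 0.5/0.1556 = 3.214, and Phi(3.214 - 1.96) = 89.5%. At -0.6: 3.857, and Phi(1.897) = 97.1%. The stated figures are reproduced to within about a point.

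**Mechanism.** With r retrieved dropouts the residual df is r - 2, and the drawn variance has mean k = (r-2)/(r-4) times its estimate: 3 at r = 5, 2 at r = 6, 1.33 at r = 10. In a pooled model with four arm intercepts and one slope, at 5 per arm, df = 20 - 5 = 15 and k = 15/13 = 1.15.

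**Hand approximation.** For an arm of n = 100 with m missing discontinuers, in units of sigma²/n²:

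- A = m + m²/r + s, where s = m²(1/m + 1/r)/(r-3) is the slope term for normally distributed baselines
- actual variance = n + A
- expected Rubin variance = n + m(k-1) + kA

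Results (r/m):

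- 5/5: A = 5 + 5 + 5 = 15; actual 115; Rubin 100 + 10 + 45 = 155; SE ratio sqrt(155/115) = 1.16
- 6/6: A = 6 + 6 + 4 = 16; actual 116; Rubin 100 + 6 + 32 = 138; ratio 1.09
- 5/10: A = 10 + 20 + 15 = 45; actual 145; Rubin 100 + 20 + 135 = 255; ratio 1.33

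This omits the scatter that noisy fitted lines add to the ANCOVA residual variance, so it should fall a little below simulation.

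**Simulation, equal counts in every arm.** Assumptions: 4 x 100, residual SD 1.1, baseline SD about 0.8, slope -0.4, the planned ANCOVA, data missing at random among discontinuers, 8000 trials each. The last two columns show separate vs pooled.

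| r/m | SE / true SD, separate | Null rejection | Power at -0.5 |
|---|---|---|---|
| 5/5 | 0.202/0.170 = 1.19 | 2.6% vs 4.7% | 73.7% vs 84.7% |
| 6/6 | 1.11 | 3.1% vs 4.8% | 78.3% vs 84.6% |
| 5/10 | 1.35 | 1.4% vs 4.4% | 51.7% vs 77.4% |
| 6/10 | 1.19 | 2.5% vs 4.5% | 66.7% vs 79.4% |

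If only the 6 mg arm is thin and the other arms have 10 retrieved, the SE excess is 10% at 5/5 and 20% at 5/10, with null rejection 3.6% and 2.5%.

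**Averaged over all trials.** Trials sent to the back-up are included; both options agree there. All rates are assumed.

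| Discontinue / retrieved | Item 1 applies | Points lost at -0.5 | Points lost at -0.6 |
|---|---|---|---|
| 10% / 50% | 11% | 0.7 | 0.3 |
| 10% / 70% | 50% | 1.2 | 0.7 |
| 12% / 50% | 29% | 2.1 | 1.1 |
| 15% / 65% | 89% | 2.4 | 1.4 |
| 15% / 50% | 61% | 4.7 | 2.5 |
| 20% / 50% | 91% | 5.5 | 3.1 |
| 20% / 40% | 68% | 7.3 | 5.6 |
| 25% / 30% | 58% | 9.2 | 8.5 |

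Across the rates tried, the 6 mg or placebo arm has 5-6 retrieved and at least as many missing, with item 1 applying, in about 4-28% of trials. In a simpler simulation without strata and region, at a true difference of -0.8 with 10-20% discontinuation and 50-70% retrieval, the averaged loss is 0.02-0.6 points.

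**Price of pooling.** Null rejection with placebo at 5/10 and the other arms at 10/5 (same simpler simulation, Monte Carlo error about 0.25 points):

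| SD in discontinuers, placebo vs active | Pooled | Separate | Complete data |
|---|---|---|---|
| equal | 4.8% | 2.7% | 5.2% |
| 1.3 vs 1.0 | 6.0% | 2.7% | 5.4% |
| 1.5 vs 0.8, slopes -0.8 vs 0 | 7.7% | 2.5% | 5.6% |

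In the last row, 7.7 - 5.6 = 2.1 points come from the imputation. With equal counts of 5/5 or 8/7 the pooled model stays at 4.3-5.5%.

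**Can blinded counts decide?** Take 40 retrieved and 16 missing in total. Under a random split over arms the loss at -0.6 is 0.6 points. With placebo at 5/10 and the active arms at 12/2, 12/2 and 11/2, the totals are the same, but power is 84.4% separate vs 94.1% pooled at -0.6, and 69.7% vs 84.4% at -0.5. In that split, with the unequal SDs and slopes of the last row above, the pooled model rejects a true null about 7.8% of the time. Blinded totals cannot separate the harmless split from the costly one.

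**The case for a change.** The case for changing is respectable. The conservatism follows from the floor of 5 and the plan's own expectation of few retrieved dropouts. The calculations agree on its size, and at 20-25% discontinuation the averaged loss is not trivial. Pooling keeps arm-specific imputed means, so the retrieved-dropout idea survives, and the separate models could be kept as a sensitivity analysis. The health authority could be told before unblinding, and the documents do not show that separate models were specifically requested.

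What stands is the mechanism and its conditional size. The remedy does not stand as a clear improvement. A common slope and variance cannot be checked on 5 people. Pooling is most attractive when placebo is thin with many missing, and that is also where its type I error is exposed. SAP 1.5 Table 1 records that the imputation method followed health-authority advice. SAP 2.4.4 dates the last Week 30 visit to 29 January 2020, so a switch would come after all primary-endpoint visits. A pooled analysis offered only as a supplement would do no harm, but it would change no confirmatory conclusion.

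**Conclusion.** This is a fair trade-off that the plan has visibly considered. It expects few retrieved dropouts and responds with a single predictor, a switch to a back-up below 5, continued follow-up after discontinuation (protocol 1.3, footnote a) and a 30-day window around the endpoint visit (SAP 2.5.4). What remains is lost precision when an arm has 5 or 6 retrieved dropouts and at least as many missing: SE about 10-40% too large, null rejection about 1-4%, and an averaged power loss per dose from about 0.3 to 9 points depending on rates the documents do not state. The error is on the conservative side.

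These figures rest on 1.1 as the residual SD (SAP 1.3 gives it as the SD of change, so this is on the pessimistic side), the same effect in discontinuers and completers, and the assumed discontinuation and retrieval ranges. Protocol 9.1 treats -0.6 as a minimum effect, so the -0.5 figures lie below the planning value. The separate per-arm models can stay as the primary method.
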